## 10 Missing Data Imputation

Missing data will be minimized through careful study monitoring. To evaluate bias associated with missing data, characteristics of subjects with missing data will be compared, when relevant, to those of subjects with study data.

The impact of missing data on the final analysis of the primary safety endpoint analysis will be evaluated using the following models:

- Ignore missing data
- Assume missing values have met the primary safety endpoint
- Assume missing values have NOT met the primary safety endpoint
- Regression analysis. Logistic regression will be used to determine baseline predictors, if any, of the occurrence of the primary safety endpoint. If predictors are found and have biologic relevance, logistic models will be used to calculate the probability of each missing subject having had a primary safety endpoint. The sum of these probabilities across all missing subjects will be used. Covariates to be examined in logistic regression models include: age, site ID, prostate volume, assigned procedure, procedure length, preoperative sexual function, baseline IPSS score, baseline MSHQ score, baseline IIEF score.
- Finally, a tipping point analysis will be performed for the primary safety endpoint. This is the number of additional events occurring in the A group (or fewer events in the T group) that would cause the study to fail to conclude safety non-inferiority.

The impact of missing data on the final analysis of the primary effectiveness endpoint analysis will be evaluated using the following models:

- Predictive models, as described above for the interim analysis effectiveness predictive calculation
- Last observation carry forward
- Assume relatively low change score, i.e., 8 points
- Assume relatively high change score, i.e., 18 points
- Assume changes consistent with the group's median change score
- Assume zero change score (though this is highly unlikely given the long history of large mean change scores with TURP and similarly large change scores in Phase II data)

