4.3 Primary Safety Endpoint Calculation

The primary safety endpoint will test the proportion of subjects meeting the primary safety endpoint through 3 months post treatment. The hypothesis of interest for the primary safety endpoint is:

$$H_0: P_C - P_T \leq -\delta$$

$$H_a: P_C - P_T > -\delta$$

where P_T and P_C represent proportions of treatment and control subjects, respectively, who meet the primary safety endpoint. Analysis of the primary safety hypothesis will be conducted using a z-test of proportions with a pooled variance and continuity correction, using a non-inferiority margin of 10% and a one-sided significance level of 0.025. If non-inferiority is established, a test for superiority at a significance level of 0.025 will be conducted. If it can be established that the rate difference is statistically greater than 0, superiority will also be claimed.

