4.7 Handling of Missing Data

All practical monitoring and follow-up steps will be taken to ensure complete and accurate data collection. Missing observations will be described in detail and evaluated for assessment of possible bias.

It is assumed that data will be missing at random. However, to examine this assumption, an analysis will be performed to compare baseline characteristics and symptomatic status (at earlier time points) between those participants with missing data and those who completed the study. Any missing observations will be described in detail and evaluated for assessment of possible bias.

For the primary effectiveness analysis, missing data will be imputed using the method of multiple imputation, with regression models that include relevant baseline covariates and the 3 month IPSS score (if available). Missing safety outcome data will be imputed using a similar multiple imputation method. A detailed description of the multiple imputation models including the full set of covariates to be used in the imputation model will be outlined in the SAP.

For the primary safety endpoint, a missing data sensitivity analysis will also be performed by comparing analyses using the following approach:

- 1). Available data only
- 2). “missing-equals-failure”
- 3). “missing-equal-success”
- 4). Last observation carried forward (LOCF)

For the primary effectiveness endpoint, a sensitivity analysis will be performed using:

- 1). LOCF
- 2). Same as baseline

In addition, a tipping point analysis will be performed for the primary study endpoints which will allow assessment of sensitivity without need for postulating any missing data mechanism. For the safety tipping point analysis, all possible combinations of missing data from the two arms will be considered, and the point at which significance is no longer achieved will be identified.

The planned sensitivity analyses for the primary outcome in the primary analysis population will be described in further detail in the SAP.

All data collected on safety or adverse events will be reported to the extent it is available, regardless of the active/withdrawn status of participants.

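### SAP section 10 drops the multiple imputation that the protocol promises for missing safety outcomes; its only model-based step sums predicted probabilities with no variance term

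*SAP*

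**What the plan says.** Protocol 4.7 sets the method: "Missing safety outcome data will be imputed using a similar multiple imputation method". It defers the specification to the SAP, which is to give "A detailed description of the multiple imputation models including the full set of covariates". Around that analysis the protocol places available data, missing as failure, missing as success and LOCF as sensitivity analyses, plus a tipping point.

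SAP section 10 opens its safety list with "The impact of missing data on the final analysis of the primary safety endpoint analysis will be evaluated using the following models". Five approaches follow: ignore missing values, count all of them as events, count none as events, a regression step, and a tipping point. None is named primary. The regression step is conditional: "If predictors are found and have biologic relevance", then "logistic models will be used to calculate the probability of each missing subject having had a primary safety endpoint". It ends: "The sum of these probabilities across all missing subjects will be used". Assigned procedure appears only among the covariates to be examined.

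The safety comparison also differs between the documents. Protocol 4.3 specifies a "z-test of proportions with a pooled variance and continuity correction", "using a non-inferiority margin of 10% and a one-sided significance level of 0.025". SAP 5.1 uses a two-sided 95% confidence interval for the difference in proportions, computed with gsDesign functions.

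**The concern.** The regression step is the only model-based entry in the SAP's list, so it stands where the protocol's multiple imputation should be. It is a different method. Multiple imputation draws each missing outcome, repeats the draw with uncertainty in the model coefficients, and carries both sources of variation into the standard error. A sum of predicted probabilities does neither. If that sum is added to the event counts over all treated men, the missing men are analysed as though they had been observed. The interval is then too narrow, and the upper limit compared with the 10-point margin errs toward declaring non-inferiority.

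The mismatch matters whatever its numerical effect. In the protocol, the complete-case and extreme-case analyses probe a stated main analysis. In the SAP that main analysis is absent, so a reader cannot tell which safety result is to be taken as the answer when outcomes are missing.

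**Working it through.** **Inputs (Protocol 4.4):** 118 Aquablation and 59 TURP; 12% loss; 156 evaluable; assumed event rates 40% and 65%; one-sided 0.025; margin 0.10.

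**1. Reproducing the design figures.** 177 × 0.88 = 155.8, so 156 evaluable (104 + 52) and 21 missing (14 + 7). For the pooled test with continuity correction:
- pooled rate = (52 × 0.65 + 104 × 0.40)/156 = 0.483
- null SE = √[0.483 × 0.517 × (1/52 + 1/104)] = 0.0849
- SE under the alternative = √(0.65 × 0.35/52 + 0.40 × 0.60/104) = 0.0817
- correction = 0.5 × (1/52 + 1/104) = 0.0144
- superiority power = Φ[(0.25 − 0.0144 − 1.96 × 0.0849)/0.0817] = 80.1%, as stated
- non-inferiority power = Φ[(0.35 − 0.0144 − 1.96 × 0.0849)/0.0817] = 98.1%; 98.8% without the correction and 99.0% unpooled, close to the stated figure of over 99%.

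**2. Standard error if the sum is counted as events.**
- From the 156 observed: 0.0817.
- With 118 and 59 treated as observed: √(0.65 × 0.35/59 + 0.40 × 0.60/118) = 0.0767.
- Ratio 0.939, about 6% too small.

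When covariates add little information the ratio is √(1 − d) for missing fraction d, and the actual one-sided level is 1 − Φ[1.96√(1 − d)]:

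| Missing | SE shortfall | One-sided level |
|---|---|---|
| 2% | 1.0% | 0.026 |
| 5% | 2.5% | 0.028 |
| 12% (planning rate) | 6.2% | 0.033 |
| 20% | 10.6% | 0.040 |

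**3. Dependence on the test.** Simulated false non-inferiority at a true 10-point difference, 104/52 observed of 118/59, TURP rates 30–65%:

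| Test | Available cases | Summed probabilities |
|---|---|---|
| Unpooled Wald | 2.3–3.0% | 3.0–3.9% |
| Score | 2.4–2.7% | 3.1–3.5% |
| Protocol's pooled test, continuity-corrected | 1.6–1.8% | 2.2–2.6% |

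Taken rate by rate, the increase is about 0.6 to 0.8 points.

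**4. Comparison with multiple imputation.** 6,000 simulated trials per scenario; 14 + 7 missing completely at random; one assumed covariate (log-odds 0.7 per SD); arm in the model; 20 imputations; Wald limits. At the design rates the summed method's mean SE is 0.0761 against a true SD of 0.0805 (ratio 0.946). Multiple imputation gives 0.0807 against 0.0805 (ratio 1.003). False non-inferiority:
- 65% v 75%: 3.8% summed, 2.9% multiple imputation, 3.0% complete cases.
- 40% v 50%: 2.8%, 2.3% and 2.4%.

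The simulation error on each figure is about 0.2 points (√(0.03 × 0.97/6000) = 0.0022).

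**5. Treatment arm.** The SAP sums over all missing men without separating the arms, and arm need not be in the model. If it is left out, both arms' missing men are predicted at roughly a common rate, so a true 10-point difference shrinks to about 0.88 × 0.10 = 0.088; the simulation also gave 0.088. Multiple imputation with the same model shrinks equally. In that scenario false non-inferiority was 3.25% summed and 2.5% with multiple imputation. Leaving arm out therefore biases the estimate toward non-inferiority, but did not by itself raise the error rate under multiple imputation.

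**The case against.** The strongest reply is that the step decides nothing. It is one of five approaches to the impact of missing data, and it runs only if biologically relevant predictors are found. Its companions include the available-case analysis, whose standard error is not understated, both extreme cases and a tipping point. That stands. A reader might infer from the 3.3% in the table that the trial's type I error is inflated, or that the whole missing-data assessment is too favourable. Neither follows, because no document makes this step the decision rule.

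Second, the SAP does not say that the sum is added to the event count over the full denominator. That also stands as a matter of text: it is an inference. It is the only evident use, since the endpoint is a comparison of two proportions and no other variance is offered, but the literal defect is that the use is unspecified.

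Third, the size depends on the test and on how much is missing. With the protocol's own test the level stays near nominal. The 12% is a sample-size allowance; Protocol 2.34 expects little missing data, the endpoint closes at 3 months, and Protocol 4.7 keeps safety data collected before withdrawal. These points limit the numerical effect. They do not answer the mismatch: the protocol promises an imputation analysis that the SAP does not contain.

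**Conclusion.** The protocol and SAP disagree on how missing primary safety outcomes are handled, and the SAP's only model-based step is deterministic single imputation. The mismatch rests on the text alone and needs no calculation.

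The variance effect rests on reading the sum as an event count, on data missing completely at random, and on covariates that add little. Under those assumptions it is modest, falls with lower missingness, and depends on the test; the score test here is a stand-in for the SAP's gsDesign functions. At the design rates simulated non-inferiority power is about 99% under every method (0.992 summed, 0.989 multiple imputation, 0.989 complete cases), so the safety conclusion would probably not change. This should be corrected, but nothing here shows that the safety result is unsound.

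**What to change.** Replace the summed-probability step in SAP section 10 with multiple imputation from a logistic model. Always include treatment arm, whether or not it is selected as a predictor. Draw the coefficients and then each missing outcome, apply the primary safety comparison to every completed dataset, and combine by Rubin's rules. The combining rule and the draws are details for the SAP to supply; a reader should not attribute them to Protocol 4.7, which asks only for multiple imputation. Name this as the safety missing-data method that Protocol 4.7 promises, and keep the other four approaches as sensitivity analyses.

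Protocol 3.1 marks this endpoint as already reported, so the multiple imputation result should be added to the record, or the departure documented. The cost is SAP wording, a little code and a slightly wider interval.

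Suggested wording: *Missing primary safety outcomes in the mITT cohort will be multiply imputed from a logistic model that always includes treatment arm and the listed baseline covariates, with draws of both coefficients and outcomes. The primary safety comparison will be applied to each completed dataset and the results combined by Rubin's rules.*
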